11.8 Study Closeout

Upon completion of the study (defined as all subjects have completed all follow-up visits, all CRFs are complete, and all queries have been resolved) the Lead PI or designee(s) at the Duke GI Oncology Clinical Trials Office will notify the Investigator of closeout and a study closeout visit will be performed.

The study monitor or study designee will ensure that the Investigator's regulatory files are up to date and complete, and that any outstanding issues from previous visits have been resolved. Other issues to be reviewed at the closeout visit include: retention of study files, possibility of site audits, publication policy, and study closure with local IRB.

11.9 Records Retention

The Investigator will maintain the records of study drug disposition, worksheets and all other study-specific documentation (e.g., study files, source documentation) until notified by the Lead PI or designee(s) at the Duke GI Oncology Clinical Trials Office that records may be destroyed. If the application is not filed or is withdrawn, the Investigator will maintain the records for at least two (2) years after the formal discontinuation of the clinical development program for this product(s).

To avoid error, the Investigator will contact the Lead PI or designee(s) at the Duke GI Oncology Clinical Trials Office before the destruction of any records pertaining to the study to ensure they no longer need to be retained. In addition, the Lead PI or designee(s) will be contacted if the Investigator plans to leave the institution so that arrangements can be made for the transfer of records.

Appendix A. RECIST 1.1

RECIST version 1.1* will be used in this study for assessment of tumor response. While either CT or MRI may be utilized, as per RECIST 1.1, CT is the preferred imaging technique in this study.

*E.A. Eisenhauer, P. Therasse, J. Bogaerts, L.H. Schwartz, D. Sargent, R. Ford, J. Dancey, S. Arbuck, S. Gwyther, M. Mooney, L. Rubinstein, L. Shankar, L. Dodd, R. Kaplan, D. Lacombe, J. Verweij. New response evaluation criteria in solid tumors: Revised RECIST guideline (version 1.1). Eur J Cancer. 2009 Jan;45(2):228-47.

Definitions

Response and progression will be evaluated in this study using the international criteria proposed by the Response Evaluation Criteria in Solid Tumors (RECIST) Committee (version 1.1). Changes in only the largest diameter (uni-dimensional measurement) of the tumor lesions are used in the RECIST criteria. Note: Lesions are either measurable or non-measurable using the criteria provided below. The term “evaluable” in reference to measurability will not be used because it does not provide additional meaning or accuracy.

Measurable Disease

Tumor lesions: Must be accurately measured in at least one dimension (longest diameter in the plane of measurement is to be recorded) with a minimum size of:

- 10mm by CT scan (irrespective of scanner type) and MRI (no less than double the slice thickness and a minimum of 10mm)
- 10mm caliper measurement by clinical exam (when superficial)
- 20mm by chest X-ray (if clearly defined and surrounded by aerated lung)

Malignant lymph nodes: To be considered pathologically enlarged and measurable, a lymph node must be ≥ 15 mm in short axis when assessed by CT scan (CT scan slice thickness recommended to be no greater than 5 mm). At baseline and in follow-up, only the short axis will be measured and followed.

Non-measurable Disease

All other lesions (or sites of disease), including small lesions (longest diameter ≥ 10 to < 15 mm with conventional techniques or < 10 mm using spiral CT scan), are considered non-measurable disease. Leptomeningeal disease, ascites, pleural or pericardial effusion, inflammatory breast disease, lymphangitic involvement of skin or lung, abdominal masses/abdominal organomegaly identified by physical exam that is not measurable by reproducible imaging techniques are all non-measurable.

Bone lesions:

- Bone scan, PET scan or plain films are not considered adequate imaging techniques to measure bone lesions. However, these techniques can be used to confirm the presence or disappearance of bone lesions.
- Lytic bone lesions or mixed lytic-blastic lesions, with identifiable soft tissue components, that can be evaluated by cross sectional imaging techniques such as CT or MRI can be considered as measurable lesions if the soft tissue component meets the definition of measurability described above.
- Blastic bone lesions are non-measurable.

Cystic lesions:

- Lesions that meet the criteria for radiographically defined simple cysts should not be considered as malignant lesions (neither measurable nor non-measurable) since they are, by definition, simple cysts.
- 'Cystic lesions' thought to represent cystic metastases can be considered as measurable lesions, if they meet the definition of measurability described above. However, if noncystic lesions are present in the same patient, these are preferred for selection as target lesions.

Lesions with prior local treatment:

- Tumor lesions situated in a previously irradiated area, or in an area subjected to other loco-regional therapy, are usually not considered measurable unless there has been demonstrated progression in the lesion. Study protocols should detail the conditions under which such lesions would be considered measurable.

Target Lesions

All measurable lesions up to a maximum of 2 lesions per organ and 5 lesions in total, should be identified as target lesions and recorded and measured at baseline. Target lesions should be selected on the basis of their size (lesions with the longest diameter), be representative of all involved organ, but in addition should be those that lend themselves to reproducible repeated measurements.

Lymph nodes merit special mention since they are normal anatomical structures which may be visible by imaging even if not involved by tumor. Pathological nodes which are defined as measurable and may be identified as target lesions must meet the criterion of a short axis of $\geq 15\text{mm}$ by CT scan. Only the short axis of these nodes will contribute to the baseline sum. The short axis of the node is the diameter normally used by radiologists to judge if a node is involved by solid tumor. Nodal size is normally reported as two dimensions in the plane in which the image is obtained (for CT scan this is almost always the axial plane; for MRI the plane of acquisition may be axial, sagittal or coronal). The smaller of these measures is the short axis. For example, an abdominal node which is reported as being $20\text{mm} \times 30\text{mm}$ has a short axis of 20mm and qualifies as a malignant, measurable node. In this example, 20mm should be recorded as the node measurement. All other pathological nodes (those with short axis $\geq 10\text{mm}$ but $< 15\text{ mm}$) should be considered non-target lesions. Nodes that have a short axis $< 10\text{mm}$ are considered non-pathological and should not be recorded or followed.

A sum of the diameters (longest for non-nodal lesions, short axis for nodal lesions) for all target lesions will be calculated and reported as the baseline sum diameters. If lymph nodes are to be included in the sum, then as noted above, only the short axis is added into the sum. The baseline sum diameters will be used as reference to further characterize any objective tumor regression in the measurable dimension of the disease.

Non-target Lesions

All other lesions (or sites of disease) including pathological lymph nodes should be identified as non-target lesions and should also be recorded at baseline. Measurements are not required and these lesions should be followed as 'present', 'absent', or in rare cases 'unequivocal progression' (more details to follow). In addition, it is possible to record multiple non-target lesions involving the same organ as a single item on the case record form (e.g. 'multiple enlarged pelvic lymph nodes' or 'multiple liver metastases').

Guidelines for Evaluation of Measurable Disease

All measurements should be recorded in metric notation, using calipers if clinically assessed. All baseline evaluations should be performed as close as possible to the treatment start and never more than 4 weeks before the beginning of the treatment.

The same method of assessment and the same technique should be used to characterize each identified and reported lesion at baseline and during follow-up. Imaging based evaluation should always be done rather than clinical examination unless the lesion(s) being followed cannot be imaged but are assessable by clinical exam.

Clinical lesions: Clinical lesions will only be considered measurable when they are superficial and >10mm diameter as assessed using calipers (e.g. skin nodules). For the case of skin lesions, documentation by color photography including a ruler to estimate the size of the lesion is suggested. As noted above, when lesions can be evaluated by both clinical exam and imaging, imaging evaluation should be undertaken since it is more objective and may also be reviewed at the end of the study.

Chest X-ray: Chest CT is preferred over chest X-ray, particularly when progression is an important endpoint, since CT is more sensitive than X-ray, particularly in identifying new lesions. However, lesions on chest X-ray may be considered measurable if they are clearly defined and surrounded by aerated lung.

CT, MRI: CT is the best currently available and reproducible method to measure lesions selected for response assessment. This guideline has defined measurability of lesions on CT scan based on the assumption that CT slice thickness is 5mm or less. When CT scans have slice thickness greater than 5 mm, the minimum size for a measurable lesion should be twice the slice thickness. MRI is also acceptable in certain situations (e.g. for body scans).

Ultrasound: Ultrasound is not useful in assessment of lesion size and should not be used as a method of measurement. Ultrasound examinations cannot be reproduced in their entirety for independent review at a later date and, because they are operator dependent, it cannot be guaranteed that the same technique and measurements will be taken from one assessment to the next. If new lesions are identified by ultrasound in the course of the study, confirmation by CT or MRI is advised. If there is concern about radiation exposure from CT, MRI may be used instead of CT in selected instances.

Endoscopy, laparoscopy: The utilization of these techniques for objective tumor evaluation is not advised. However, they can be useful to confirm complete pathological response when biopsies are obtained or to determine relapse in trials where recurrence following complete response or surgical resection is an endpoint.

Tumor markers: Tumor markers alone cannot be used to assess objective tumor response. If markers are initially above the upper normal limit, however, they must normalize for a patient to be considered in complete response. Because tumor markers are disease specific, instructions for their measurement should be incorporated into protocols on a disease specific basis. Specific guidelines for both CA-125 response (in recurrent ovarian cancer) and PSA response (in recurrent prostate cancer), have been published. In addition, the Gynecologic Cancer Intergroup has developed CA125 progression criteria which are to be integrated with objective tumor assessment for use in first-line trials in ovarian cancer.

Cytology, histology: These techniques can be used to differentiate between PR and CR in rare cases if required by protocol (for example, residual lesions in tumor types such as germ cell tumors,

where known residual benign tumors can remain). When effusions are known to be a potential adverse effect of treatment (e.g. with certain taxane compounds or angiogenesis inhibitors), the cytological confirmation of the neoplastic origin of any effusion that appears or worsens during treatment can be considered if the measurable tumor has met criteria for response or stable disease in order to differentiate between response (or stable disease) and progressive disease.

Response Criteria

Evaluation of Target Lesions

- Complete Response (CR): Disappearance of all target lesions. Any pathological lymph nodes (whether target or non-target) must have reduction in short axis to <10 mm.
- Partial Response (PR): At least a 30% decrease in the sum of diameters of target lesions, taking as reference the baseline sum diameters.
- Progressive Disease (PD): At least a 20% increase in the sum of diameters of target lesions, taking as reference the smallest sum on study (this includes the baseline sum if that is the smallest on study). In addition to the relative increase of 20%, the sum must also demonstrate an absolute increase of at least 5 mm. (Note: the appearance of one or more new lesions is also considered progression).
- Stable Disease (SD): Neither sufficient shrinkage to qualify for PR nor sufficient increase to qualify for PD, taking as reference the smallest sum diameters while on study.

Lymph nodes. Lymph nodes identified as target lesions should always have the actual short axis measurement recorded (measured in the same anatomical plane as the baseline examination), even if the nodes regress to below 10 mm on study. This means that when lymph nodes are included as target lesions, the 'sum' of lesions may not be zero even if complete response criteria are met, since a normal lymph node is defined as having a short axis of <10 mm. Case report forms or other data collection methods may therefore be designed to have target nodal lesions recorded in a separate section where, in order to qualify for CR, each node must achieve a short axis <10 mm. For PR, SD and PD, the actual short axis measurement of the nodes is to be included in the sum of target lesions.

Target lesions that become 'too small to measure'. While on study, all lesions (nodal and non-nodal) recorded at baseline should have their actual measurements recorded at each subsequent evaluation, even when very small (e.g. 2 mm). However, sometimes lesions or lymph nodes which are recorded as target lesions at baseline become so faint on CT scan that the radiologist may not feel comfortable assigning an exact measure and may report them as being 'too small to measure'. When this occurs it is important that a value be recorded on the case report form. If it is the opinion of the radiologist that the lesion has likely disappeared, the measurement should be recorded as 0mm. If the lesion is believed to be present and is faintly seen but too small to measure, a default value of 5mm should be assigned (Note: It is less likely that this rule will be used for lymph nodes since they usually have a definable size when normal and are frequently surrounded by fat such as in the retroperitoneum; however, if a lymph node is believed to be present and is faintly seen but too small to measure, a default value of 5 mm should be assigned in this circumstance as well). This default value is derived from the 5 mm CT slice thickness (but should not be changed with varying CT slice thickness). The measurement of these lesions is potentially non-reproducible, therefore providing this default value will prevent false responses or progressions based upon measurement error. To reiterate, however, if the radiologist is able to provide an actual measure, that should be recorded, even if it is below 5 mm.

Lesions that split or coalesce on treatment. When non-nodal lesions 'fragment', the longest diameters of the fragmented portions should be added together to calculate the target lesion sum. Similarly, as lesions coalesce, a plane between them may be maintained that would aid in obtaining maximal diameter measurements of each individual lesion. If the lesions have truly coalesced such that they are no longer separable, the vector of the longest diameter in this instance should be the maximal longest diameter for the 'coalesced lesion'.

Evaluation of Non-target Lesions

While some non-target lesions may actually be measurable, they need not be measured and instead should be assessed only qualitatively at the time points specified in the protocol.

- Complete Response (CR): Disappearance of all non-target lesions and normalization of tumor marker level. All lymph nodes must be non-pathological in size (<10mm short axis).
- Non-CR/Non-PD: Persistence of one or more non-target lesion(s) and/or maintenance of tumor marker level above the normal limits.
- Progressive Disease (PD): Unequivocal progression (see comments below) of existing non-target lesions. (Note: the appearance of one or more new lesions is also considered progression).

When the patient also has measurable disease. In this setting, to achieve 'unequivocal progression' on the basis of the non-target disease, there must be an overall level of substantial worsening in non-target disease such that, even in presence of SD or PR in target disease, the overall tumor burden has increased sufficiently to merit discontinuation of therapy. A modest 'increase' in the size of one or more non-target lesions is usually not sufficient to qualify for unequivocal progression status. The designation of overall progression solely on the basis of change in non-target disease in the face of SD or PR of target disease will therefore be extremely rare.

When the patient has only non-measurable disease. This circumstance arises in some phase III trials when it is not a criterion of study entry to have measurable disease. The same general concept apply here as noted above, however, in this instance there is no measurable disease assessment to factor into the interpretation of an increase in non-measurable disease burden. Because worsening in non-target disease cannot be easily quantified (by definition: if all lesions are truly non-measurable) a useful test that can be applied when assessing patients for unequivocal progression is to consider if the increase in overall disease burden based on the change in non-measurable disease is comparable in magnitude to the increase that would be required to declare PD for measurable disease: i.e. an increase in tumor burden representing an additional 73% increase in 'volume' (which is equivalent to a 20% increase diameter in a measurable lesion). Examples include an increase in a pleural effusion from 'trace' to 'large', an increase in lymphangitic disease from localized to widespread, or may be described in protocols as 'sufficient to require a change in therapy'. If 'unequivocal progression' is seen, the patient should be considered to have had overall PD at that point. While it would be ideal to have objective criteria to apply to non-measurable disease, the very nature of that disease makes it impossible to do so, therefore the increase must be substantial.

New Lesions

The appearance of new malignant lesions denotes disease progression; therefore, some comments on detection of new lesions are important. There are no specific criteria for the identification of new radiographic lesions; however, the finding of a new lesion should be unequivocal: i.e. not attributable to differences in scanning technique, change in imaging modality or findings thought to represent something other than tumor (for example, some 'new' bone lesions may be simply healing or flare of pre-existing lesions). This is particularly important when the patient's baseline

lesions show partial or complete response. For example, necrosis of a liver lesion may be reported on a CT scan report as a 'new' cystic lesion, which it is not.

A lesion identified on a follow-up study in an anatomical location that was not scanned at baseline is considered a new lesion and will indicate disease progression. An example of this is the patient who has visceral disease at baseline and while on study has a CT or MRI brain ordered which reveals metastases. The patient's brain metastases are considered to be evidence of PD even if he/she did not have brain imaging at baseline.

If a new lesion is equivocal, for example because of its small size, continued therapy and follow-up evaluation will clarify if it represents truly new disease. If repeat scans confirm there is definitely a new lesion, then progression should be declared using the date of the initial scan.

While FDG-PET response assessments need additional study, it is sometimes reasonable to incorporate the use of FDG-PET scanning to complement CT scanning in assessment of progression (particularly possible 'new' disease). New lesions on the basis of FDG-PET imaging can be identified according to the following algorithm:

- Negative FDG-PET at baseline, with a positive FDG-PET at follow-up is a sign of PD based on a new lesion.
- No FDG-PET at baseline and a positive FDG-PET at follow-up: If the positive FDG-PET at follow-up corresponds to a new site of disease confirmed by CT, this is PD. If the positive FDG-PET at follow-up is not confirmed as a new site of disease on CT, additional follow-up CT scans are needed to determine if there is truly progression occurring at that site (if so, the date of PD will be the date of the initial abnormal FDG-PET scan). If the positive FDG-PET at follow-up corresponds to a pre-existing site of disease on CT that is not progressing on the basis of the anatomic images, this is not PD.

Evaluation of Best Overall Response

The best overall response is the best response recorded from the start of the study treatment until the end of treatment taking into account any requirement for confirmation. On occasion a response may not be documented until after the end of therapy so protocols should be clear if post-treatment assessments are to be considered in determination of best overall response. Protocols must specify how any new therapy introduced before progression will affect best response designation. The patient's best overall response assignment will depend on the findings of both target and non-target disease and will also take into consideration the appearance of new lesions. Furthermore, depending on the nature of the study and the protocol requirements, it may also require confirmatory measurement. Specifically, in non-randomised trials where response is the primary endpoint, confirmation of PR or CR is needed to deem either one the "best overall response."

The best overall response is determined once all the data for the patient is known. Best response determination in trials where confirmation of complete or partial response IS NOT required: Best response in these trials is defined as the best response across all time points (for example, a patient who has SD at first assessment, PR at second assessment, and PD on last assessment has a best overall response of PR). When SD is believed to be best response, it must also meet the protocol specified minimum time from baseline. If the minimum time is not met when SD is otherwise the best time point response, the patient's best response depends on the subsequent assessments. For example, a patient who has SD at first assessment, PD at second and does not meet minimum duration for SD, will have a best response of PD. The same patient lost to follow-up after the first SD assessment would be considered inevaluable.

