5.7 Subject Discontinuation

Subjects will receive study treatment until treatment discontinuation for one of the reasons listed below. However, subjects may discontinue study treatment or withdraw their consent to participate in the study at any time without prejudice. All reasons for discontinuation or withdrawal from trial will be recorded.

The maximum duration of treatment for pembrolizumab will be up to 35 cycles. The duration of treatment for XELOX will be until unacceptable drug-related toxicity or disease progression. If capecitabine is not tolerated, monotherapy with pembrolizumab may be continued. Patients who complete 35 cycles of therapy and have complete response or prolonged stable disease may also elect to end therapy with capecitabine after a discussion with their treating physician and with approval of the PI. Re-introduction of oxaliplatin is permitted provided that neuropathy has improved. Reasons for subject discontinuation by the Investigator may include, but are not limited to, the following:

- Death
- Confirmed radiographic disease progression (Note: With approval of the Lead PI, a subject may be granted an exception to continue on study treatment with confirmed radiographic progression if clinically stable or clinically improved.)
- Significant noncompliance by subject or Investigator
- Investigator or Lead PI determination that it is no longer safe and/or no longer in the subject's best interest to continue participation
- Withdrawal of consent
- Lost to follow-up
- Necessity for treatment with other anticancer treatment prohibited by protocol
- Sexually active subjects who refuse to use medically accepted methods of contraception during the course of the study and for 120 days following the last dose of study drug
- Women who become pregnant or are breast feeding
- Request by regulatory agencies for termination of treatment of an individual subject or all subjects under the protocol
- The following **Treatment-Related Discontinuation Criteria** attributed to pembrolizumab:
 - Any Grade 2 uveitis, eye pain, or blurred vision that does not respond to topical therapy and does not improve to Grade 1 OR requires systemic treatment.
 - Recurrent Grade 2 pneumonitis
 - Any Grade 3 non-skin adverse event lasting > 7 days, with the following exceptions for treatment-related laboratory abnormalities, uveitis, pneumonitis, bronchospasm, diarrhea, colitis, neurologic toxicity, hypersensitivity reactions, and infusion reactions:

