- NOTE:** After Cycle 1, the treating physician may choose to hold oxaliplatin and continue capecitabine and pembrolizumab at current dose as clinically indicated. If toxicity resolves to grade 1 or less the treating physician may choose to restart oxaliplatin later in the patient's treatment course, the dose of oxaliplatin at which the patient restarts should be one dose level lower than last dose level on which patient was treated. The specific treatment approach used and dose modifications that occur are required to be reported in the Case Report Forms.

If grade 2 intolerable, grade 3 or grade 4 neurological toxicity (see Table 3E) is evident at the time of the next planned administration of oxaliplatin, then oxaliplatin administration will be held until the next treatment cycle. Capecitabine and pembrolizumab will be administered if otherwise appropriate.

Missed doses will not be made up. If toxicity resolves to grade 1 or less at next treatment cycle, resume oxaliplatin per instructions provided in Table 3E. If neurological toxicity is still present and has not resolved to grade 1 or less at the next treatment cycle, oxaliplatin will continue to be held. Patients may continue to receive capecitabine and pembrolizumab on study if otherwise appropriate.

Oxaliplatin may be repeatedly temporarily discontinued and then re-initiated in this fashion unless the patient has disease progression, whereby the patient will be removed from the study. However, if the patient is not receiving oxaliplatin at the time of progression, if it is appropriate and safe as determined by the treating physician that oxaliplatin can be restarted, oxaliplatin may be restarted and the patient may continue on treatment. If the patient has disease progression on oxaliplatin or it is not safe or appropriate to restart oxaliplatin, the patient will be removed from the study.

Dose escalations of oxaliplatin are not permitted at any time.

Laryngopharyngeal Dysesthesia

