9.1.2 Secondary Endpoints

Secondary endpoints include the safety and tolerability of the XELOX/pembrolizumab regimen and response rate (RR). Adverse events will be described and presented by Type and Grade according to NCI-CTCAE version 4.03 criteria and descriptively compared with historical controls.

Radiographic imaging will be repeated every three cycles (approximately every 9 weeks) as described in Section 5.0. Tumor response defined as complete response (CR) or partial response (PR) will be assessed using RECIST 1.1 (see Section 5.6).

RR will be estimated by the 90% confidence interval for the binomial proportion. With 35 patients studied (5 in the safety validation and 30 in the expanded cohort), RR can be estimated to within at most +/- 0.14 with 90% confidence.

The magnitude of reduction in tumor burden will be summarized descriptively (such as with a waterfall plot) based on change in the sum of the longest diameters of target lesions relative to baseline.

Overall survival (OS) will be described.

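### The RECIST 1.1 response window does not close at progression although treatment may continue past it, so post-progression responses can raise the response rate; the waterfall sum also differs from the RECIST sum for nodes

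*Combined protocol and SAP*

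**What the plan says.** **Response window.** Section 9.1.2 counts CR or PR by RECIST 1.1 and refers to Section 5.6, which refers to Appendix A. There, the part headed Evaluation of Best Overall Response sets the window as follows: "The best overall response is the best response recorded from the start of the study treatment until the end of treatment". For trials that do not require confirmation it adds: "Best response in these trials is defined as the best response across all time points". Neither Section 9 nor Appendix A ends the window at progression.

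**Treatment after progression.** Treatment normally stops at progression (Synopsis, Section 5.2), with two exceptions. Under Section 5.7, with Lead PI approval, "a subject may be granted an exception to continue on study treatment with confirmed radiographic progression if clinically stable or clinically improved". Under Section 7.2.1.2.1, for a patient not receiving oxaliplatin when progression occurs, "oxaliplatin may be restarted and the patient may continue on treatment" if the treating physician judges this safe and appropriate. Section 5.6.2 also warns that stopping at a first apparent progression may be too early. It adopts irRC to capture responses after progression that RECIST misses.

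**Waterfall plot.** Sections 9.1.1 and 9.1.2 both describe a plot "based on change in the sum of the longest diameters of target lesions relative to baseline". For lymph nodes Appendix A says "only the short axis will be measured and followed" and "Only the short axis of these nodes will contribute to the baseline sum".

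**The concern.** A best-response window that runs to the end of treatment does no harm when treatment ends at progression. Here it need not. A patient can progress by RECIST, stay on treatment under either exception, shrink later, and enter the numerator of the response rate. The error can only go upward, the confidence interval does not cover it, and a single-arm trial has no control group with the same window to compare against.

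The waterfall plot is a separate and smaller matter. It is meant to show the same tumor shrinkage that determines RECIST response, but as worded it adds up a different quantity whenever a target lesion is a node. A reader could then see a RECIST responder whose bar stops short of the 30% line.

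**Working it through.** **1. The plan's own precision figure.** Inputs from 9.1.2: n = 35, 90% confidence, worst case p = 0.5. Half-width = 1.645 × √(0.25/35) = 0.139, which matches the stated 0.14. The point raised here does not change it.

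**2. Which best-response rule applies.** Appendix A calls for confirmation of CR or PR in non-randomised trials where response is the primary endpoint. Here PFS is primary, response is secondary, and Section 9 states no confirmation rule. The branch that takes the best response over all time points therefore applies.

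**3. Can a RECIST PR follow a RECIST PD?** Section 5.6.1 measures PD from the smallest sum on study (at least +20% and +5 mm) and PR from baseline (at least −30%). An illustrative target-lesion sum:

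| Assessment | Sum (mm) | Change | Category |
|---|---|---|---|
| Baseline | 100 | – | – |
| Nadir | 80 | −20% from baseline | SD |
| Next | 100 | (100 − 80)/80 = +25%, +20 mm from nadir | PD |
| Later, still on treatment | 65 | (65 − 100)/100 = −35% from baseline | PR |

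This patient had no response before progression and is a responder under the written rule.

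**4. Effect on the response rate.** Each such patient adds 1/35 = 2.9 points. The documents give no frequency, so the number of cases k is an assumption. The starting count of 14/35 is also assumed, for illustration.

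| k | Added points (k/35) | From 14/35 = 40.0% |
|---|---|---|
| 0 | 0 | 40.0% |
| 1 | 2.9 | 42.9% |
| 2 | 5.7 | 45.7% |
| 3 | 8.6 | 48.6% |

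Against the half-width of 13.9 points, one case is 2.9/13.9 = 21% and three are 8.6/13.9 = 62%.

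**5. Waterfall sum against RECIST sum.** Assumed lesions: a liver lesion shrinks from 40 to 28 mm, and a node from 20 × 30 to 14 × 27 mm.

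- Appendix A sum (short axis for the node): (28 + 14)/(40 + 20) − 1 = 42/60 − 1 = −30.0%, which meets PR.
- Longest-diameter sum: (28 + 27)/(40 + 30) − 1 = 55/70 − 1 = −21.4%, which does not reach the 30% line.

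The same patient is a responder in the table and not in the plot.

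**The case against.** The strongest reply is that the plan already separates the two kinds of response. Section 5.6.2 says irRC is there for responses after progression, and 9.1.2 limits the response rate to RECIST 1.1. On that reading post-progression responses never enter the response rate. This is a fair account of the likely intent, but no text carries it out: the RECIST window is never closed, and 9.1.2 leads to Appendix A without qualification.

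A second reply is that the Appendix A sentence is generic guideline text. That is so. The same paragraphs tell protocols to be clear about post-treatment assessments and to specify how new therapy before progression is handled. Section 9 does neither, so the generic sentence is the only rule there is.

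Third, the route is narrow, and this stands. One exception needs Lead PI approval and the other applies only to patients off oxaliplatin at progression. Progression by a new lesion makes a later RECIST response unlikely while that lesion persists. Patients already in PR before progression add nothing. Oxaliplatin is also part of the protocol regimen, so a response after it is restarted is not a response to some other treatment. The objection is to its timing after progression.

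On the waterfall, a reader might infer that longest diameters of nodes will not exist and the plot cannot be drawn. The documents do not support that. The RECIST record holds only the short axis, but irRC (Appendix B) needs two perpendicular diameters of index lesions, so a longest diameter may be available. The plan does not say the plot would use it, and if it did, the mismatch with the RECIST sum would remain. Appendix A itself speaks loosely of the largest diameter before refining this for nodes, so the waterfall wording may be shorthand.

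**Conclusion.** Both parts hold as faults of definition. As written, a RECIST PD followed by a PR on continued treatment counts towards the response rate. Each case is worth 2.9 points, and 0 to 3 cases, an assumed range, give 0 to 8.6 points. The number is unknown and probably small.

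A reader might infer that the response rate will be inflated, or that the plan deliberately counts post-progression responses. Neither follows: the documents give no rate of continuation or later response, and Section 5.6.2 points the other way. What the documents support is that the rule can raise the response rate and cannot lower it.

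The consequence is limited. The response rate is secondary and descriptive, with no null value or decision rule, and PFS, the sample size and the stated ±0.14 are untouched. The waterfall mismatch affects only a descriptive display and arises only for patients with nodal target lesions. The change is still worth making, because response rate is a named secondary objective and the correction is cheap.

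**What to change.** **Response rate (9.1.2).** Define best overall response for this endpoint as the best RECIST 1.1 response from the start of treatment to the earliest of:

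- first RECIST 1.1 progression;
- start of new anti-cancer therapy;
- end of treatment.

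State that this definition overrides the generic window in Appendix A, so that the two do not contradict each other. It also settles the two matters Appendix A leaves to the protocol: new therapy and post-treatment scans. Report responses that first appear after RECIST progression separately, under irRC.

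**Waterfall plot (9.1.1 and 9.1.2).** Replace the sum of longest diameters by the Appendix A target-lesion sum: longest diameter for non-nodal lesions, short axis for nodal ones.

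**Cost.** Statistical wording only. No visit, scan or treatment rule changes. The response rate may be slightly lower than under the present text.
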